	
neurologic AE since this could occur because of tissue trauma and inflammation from the surgery.
 
 
○ Sensory deficits or clinically significant persistent sensory change beyond the area proximal to the incision at time of discharge, such as allodynia or hyperalgesia, must be designated as a neurologic AE. Subjects will be followed until there is full return to baseline for the neurosensory assessment or until there is a determination that it has reached a resolution or establishment of a new baseline.
 
● ECGs, standard clinical labs at screening and T96h post-treatment [except as noted for pregnancy test]. The Investigator is responsible for determining if out of range laboratory values are clinically significant or not. All clinically significant values will be recorded in the eCRF and followed until resolution.             
 
○ ECG at screening and T24h ±2 hr
 
○ Hematology at screening and T96h: hemoglobin, hematocrit, white blood cell count with differential, red blood cell count, platelet count,
 
○ Blood Chemistry at screening and T96h: Alanine aminotransferase (ALT; SGPT) and Aspartate aminotransferase (AST; SGOT), total bilirubin (TBili), gamma-glutamyl transferase (GGT), blood urea nitrogen (BUN), creatinine, alkaline phosphatase (ALK), lactate dehydrogenase (LDH), sodium, potassium, calcium, chloride and glucose.
 
○ Serum and urine pregnancy test for FCBP: βhCG test at screening and urine test usually to be done within 24 hours prior to surgery.
 
○ Urinalysis at screening and T96h: including macroscopic analysis and, if indicated, microscopic analysis.
 
 
 

Primary Endpoint:
	
Weighted sum of pain intensity (SPI) assessments = Area Under the Curve (AUC) of the NRS current pain intensity scores from T0 to 96h at rest (<math>AUC_{0\text{ to }96h}</math>).

Key Secondary Endpoints:
	
The key secondary endpoints are:
 
 
● Percentage of subjects who do not require opioids or are opioid free (OF) from T0 to T96: <math>OF_{0\text{ to }96h}</math>
 
● Total opioid consumption (in daily oral morphine equivalents) = OC from T0 to T96h: <math>OC_{0\text{ to }96h}</math>
 
● Using NRS at rest: <math>AUC_{0\text{ to }W1}</math>
 

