#### 4. TABLE 1. SCHEDULE OF ASSESSMENTS

Assessment	Screening	In Patient							Follow-Up				Unscheduled Visit	Early Termination
		Prior to Surgery	Surgery	Post-Surgery	24h	48h	72h	96h	8±1 days	15±2 days	29±2 days	36±2 days 		
Study Day	-45 to -1	0	0	0	1	2	3	4						
Informed Consent	X	X												
Screening Medical and Surgical History	X	X												
Inclusion/Exclusion Criteria	X	X												
Screens for alcohol/drugs of abuse	X	X												
Enroll/Randomize		X												
Demographics	X													
Subject Pain Assessment Training	X													
Surgery			X											
Study treatment Infiltration/institution			X											
Pregnancy Test	X  (serum)	X  (urine)												
Vital Signs	X	X		X 	X 	X 	X 	X 	X	X	X			X
Physical Examination 	X 	X 						X 	X 	X 	X 			X
12-Lead ECG	X				X 									
Surgical Site assessment								X 	X	X	X	X	X	X
Neurosensory Exam	X							X 	X	X	X	X	X	X
Blood draw for hematology and serum chemistry	X	X 						X 						
Urine sample for urinalysis	X	X						X 						
X-ray of surgical site	X										X			X
Concomitant Medication Assessment	X	X		X	X	X	X	X	X	X	X	X	X	X
Adverse Event Assessment	X	X	X	X	X	X	X	X	X	X	X	X	X	X
NRS pain assessments				X 	X 	X 	X 	X 	X	X				X
Subject home diary record (NRS)								X	X 	X 				X
Paper Diary (review, distribution and/or collection)								X 	X 	X 				X

Assessment	Screening	In Patient							Follow-Up				Unscheduled Visit	Early Termination
		Prior to Surgery	Surgery	Post-Surgery	24h	48h	72h	96h	8±1 days	15±2 days	29±2 days	36±2 days 		
Study Day	-45 to -1	0	0	0	1	2	3	4						
Subject home diary (analgesic consumption)								X	X 	X 				X
Dispense outpatient opioid rescue if needed								X 						
PGE assessment								X	X	X	X			X
IGE assessment								X	X	X	X			X
Blood draw for PK analysis		X		X 	X 									

1. Day 36 visit will occur if insufficient wound healing is assessed by the Investigator at the Day 29 visit.
2. Note pregnancy tests are for FCBP; urine pregnancy test is to be performed within 24 hours of scheduled surgery

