3. Vital signs: 1, 2, 4, 6, 12, 24 and every 8 hours thereafter (if awake at time of assessment between the hours of 00:00 and 06:00) until discharge from the inpatient unit (may not miss two consecutive assessments). There will be a ±5-minute window allowed for the collection of vital signs in the first 4 hours after the end of surgery, after which will be a ±15-minute window allowed.
4. A complete medical history and physical examination including all major body systems will be performed at Screening. In addition, at the following times, an interim medical history and targeted physical examination will be performed prior to surgery (if not done on D-1), and to capture changes after Surgery, at 96 hours (within 4 hours of discharge), and Day 8, Day 15 and Day 29 after the administration of study medication or if the subject terminates early, at that time if allowed. Body weight (kg), in indoor clothing, but without shoes, will be measured at Screening, at 96 hours and Day 29, or at the time of discontinuation. Height (in cm) will be measured and BMI will be calculated at Screening only.
5. Post-Surgery ECG should be performed at 24 hours (±2 hours) after study medication administration
6. Surgical Site assessment: 96 hours (±4 hours) after study medication administration but prior to discharge from the inpatient unit
7. Neurosensory Exam of the Foot / Great toe (bilateral): 96 hours after study medication administration but within 4 hours of discharge from the inpatient unit
8. Clinical Laboratory tests (chemistry, hematology, and urinalysis) should be performed at screening (note if not done during screening, then perform prior to surgery) and prior to discharge from the inpatient unit (Lab collection window for 96h is ±30 min)

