- Record vital signs: 1, 2, 4, 6, 12, 24 and every 8 hours thereafter (if awake at time of assessment between the hours of 00:00 and 06:00) until discharge from the inpatient unit (may not miss two consecutive assessments). There will be a  $\pm 5$  minute window allowed for the collection of vital signs in the first 4 hours after the end of surgery, after which will be a  $\pm 15$  minute window allowed. Daily temps can be recorded along with vital signs per site SOPs at 1, 2, 4, 6, 12, 24, and every 8 h thereafter until discharge from the inpatient facility (if awake at the time of assessment between hours of midnight and 6 a.m.).
- Perform interim PE: surgical site assessment and neurosensory exam of the foot proximal to the surgical site with contralateral comparison prior to discharge from the inpatient unit.

- Perform ECG: at 24 ( $\pm$ 2) hours after surgery.
- Clinical laboratory tests (chemistry, hematology and urinalysis): at 96 hours prior to discharge from the inpatient unit.
- If the subject is participating in the PK study, obtain whole blood for PK analyses: at baseline (within the 30 min before the start of study treatment dosing), and T5min, T10 min, T15min, T30min, T45min, and T1, T1.5, T2, T2.5, T3, T4, T6, T8, T12, T16, and T24h, for a total of 17 samples).
- Subjects with inadequately controlled pain may request and receive rescue medication at any time; however, subjects will be encouraged to receive rescue only for an NRS  $\geq$  4. Additionally, subjects should be encouraged to wait at least 1 hour after completion of surgery (EOS) before utilizing pain rescue medication, if possible. NRS must be completed within 15 minutes prior to use of pain rescue medication if the time between rescue request and consumption is prolonged.
- Document the time to first use of rescue medication after T0 (between T0 and T24h) and after T24 (between T24h and T96h).
- Document concomitant medication use including doses and times taken
- All AEs that occur from the time a subject's informed consent but prior to study treatment will be captured in the medical history. All AEs and SAEs will be documented and followed from the time of administration of study treatment and will be considered treatment-emergent AEs (TEAEs).

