### **10.3. Removal of Subjects from Therapy or Assessment**

A subject is free to withdraw consent and discontinue participation in the study at any time for any reason. A subject's participation must therefore be terminated immediately upon his/her request, and the reason(s) for discontinuation appropriately documented.

A subject may be discontinued from the study for any of the following reasons:

- Safety reasons, including AEs or significant concomitant illness, injury, or urgent surgeries/procedures that would, in the judgment of the investigator, affect assessments of clinical status to a significant extent, require discontinuation of study treatment, or both
- At the request of the Sponsor, regulatory agency, or Institutional Review Board (IRB)
- Subject is lost to follow-up
- Subject treatment allocation is unblinded (i.e., individual code break; [Section 11.5](#))
- Death of subject
- A subject may also be discontinued from the study, at the discretion of the investigator and/or Sponsor, for any of the following reasons:
  - Subject refuses or is unable to adhere to the study protocol
  - Major protocol violation
  - Pregnancy
  - Use of unacceptable concomitant medication(s)
  - It is not considered in the best interest of the subject to continue
  - Administrative reasons (e.g., termination of enrollment or study)

The Investigator must maintain a record of all subjects who discontinue from the study prior to completion; the reason(s) for study discontinuation will be documented. If a subject chooses to

withdraw from the study, the Investigator should make a reasonable attempt to obtain and record the reason(s) for withdrawal in as much detail as possible, although the subject is not obligated to provide such a reason.

If a subject is discontinued while at the clinical site, the early termination procedures should be performed prior to discharge from the clinical site. The investigator should ask the subject to participate in follow-up procedures, provided that the subject has not withdrawn consent for such procedures. If the subject refuses to complete early termination/follow-up procedures or continued data collection, this information will be recorded.

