**Table 6. Clinical Laboratory Assessments**

Hematology	Chemistry
Hematocrit	Sodium
Hemoglobin	Potassium
Red blood cell (RBC) count	Calcium
Total and differential (absolute) white blood cell count	Chloride
Platelet count	Glucose
	Creatinine
	Blood urea nitrogen
	Total bilirubin
	Alanine aminotransferase (ALT)
	Aspartate aminotransferase (AST)
	Lactic dehydrogenase (LDH)
	Gamma-glutamyl transferase (GGT)
	Alkaline phosphatase

It is the responsibility of the Investigator to review and sign all lab reports expeditiously, and to document appropriate safety monitoring of study subjects. The Investigator should sign and date each lab report concurrent with her or his review, and should indicate the clinical significance of each abnormal/flagged value by noting “NCS” (not clinically significant) or “CS” (clinically significant), for example. Notations indicating that a value is clinically significant should also include a brief description of the underlying disease or condition that is associated with the value, e.g., “CS/mild anemia.” In general, and as determined by the investigator, abnormal, clinically significant laboratory values are expected to be associated with an item recorded in

medical history or with an AE. The investigator may use [Appendix 1H](#) (severity assessments of labs) to assist in the determination of clinical significance.

The clinical laboratory tests will be completed at Screening and at T96h before discharge from the inpatient unit (see). In addition to the clinical laboratory tests, a serum pregnancy test will be performed at the Screening Visit and a urine pregnancy test will be performed prior to surgery for women of childbearing potential. ALT or AST > 3x upper limit normal range (ULN) / Tot. Bili > 3 X ULN/ Alk Phos. >2X ULN will be considered an adverse event, as well as any other changes deemed clinically significant by the Investigator.

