8.8 Clinical Laboratory Evaluation

Clinical laboratory tests (blood chemistry, hematology and urinalysis) will be collected at screening and before discharge from the inpatient unit (T96h). All results will be listed. For each individual lab test value, the raw value and change from screening will be summarized by treatment.

Each clinical laboratory test will be defined by the clinical laboratory to be “Low”, “Normal”, or “High”, according to the normal reference range from the clinical laboratory. The number and percentage of subjects who have a shift from within to outside the normal reference range from screening to T96h will be summarized by treatment.

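### No post-dose hematology, chemistry or urinalysis is required for a subject who leaves the inpatient unit before T96h

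*Protocol*

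**What the plan says.** In Protocol Table 1, the rows "Blood draw for hematology and serum chemistry" and "Urine sample for urinalysis" are marked at screening, before surgery and at 96h. Both are blank in every other column, including Unscheduled Visit and Early Termination. Footnote 8 asks for the tests at screening "and prior to discharge from the inpatient unit (Lab collection window for 96h is ±30 min", so the post-dose tests come before discharge, with a window of 30 minutes either side of 96h.

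The text sections agree with the table:
- Synopsis, safety assessment times: "Hematology at screening and T96h", with the same two times for chemistry and urinalysis.
- Section 9.1.4: "Clinical laboratory tests (chemistry, hematology and urinalysis): at 96 hours prior to discharge from the inpatient unit".
- Section 12.5.1: "The clinical laboratory tests will be completed at Screening and at T96h before discharge from the inpatient unit".

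On leaving early, Section 10.3 says: "If a subject is discontinued while at the clinical site, the early termination procedures should be performed prior to discharge from the clinical site". Section 9.1.9 lists those procedures as vital signs, surgical site and neurosensory examination, concomitant medication and treatment, and adverse events. The synopsis visit schedule says in general terms that safety and subject-reported assessments are done at the early termination visit.

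SAP 8.8 lists all laboratory results and summarizes values and changes from screening. It also counts subjects with a "shift from within to outside the normal reference range from screening to T96h".

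**The concern.** Clinical laboratory results are a named safety endpoint (Protocol 12.6.2), and the Safety Population is everyone who received any part of a dose. The schedule attaches the only required post-dose sample to a time that a subject who leaves early does not reach. Some of those subjects leave because of an adverse event or an intercurrent illness, and in them a laboratory change would be most informative.

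Two things are at stake. First, the thresholds for transaminases, bilirubin and alkaline phosphatase that Section 12.5.1 treats as adverse events can be applied only if a sample is taken. Second, the shift table in SAP 8.8 would describe subjects who stayed 96 hours, while its nominal denominator is all dosed subjects. Earlier exposure is limited: Protocol Table 2 shows 29 subjects on active drug in the Phase 1 study, six of them at 4.2 mg. The missing values are few, but so are the values they would join.

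**Working it through.** No figure in the plan bears on this point, so there is none to reproduce. The check is a comparison of the sections, followed by a rough size.

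**1. Which safety assessments are carried to early termination?**

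| Assessment | Timing in Protocol 12.5 | Early Termination column, Table 1 |
|---|---|---|
| X-ray (12.5.3) | screening, D29/ET | marked |
| Physical examination (12.5.6) | includes D29/ET | marked |
| Surgical site (12.5.7) | T96h, D8, D15, D29/ET | marked |
| Neurosensory exam (12.5.8) | includes D29/ET | marked |
| ECG (12.5.5) | screening, T24h | blank |
| Hematology, chemistry, urinalysis (12.5.1) | screening, T96h | blank |

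The table and the text agree row by row, so the blank laboratory cells are unlikely to come from the way the table was read. ECG is also not carried over, but it is due at T24h; a subject leaving between T24h and T96h has the ECG and not the laboratory tests.

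**2. Does footnote 8 cover an early exit?** Footnote 4 to the same table shows how the protocol words such a rule: it places the examination at the time of early termination if the subject allows, and body weight at the time of discontinuation. Footnote 8 has no equivalent. Its only stated window is the one around 96h, and Sections 9.1.4 and 12.5.1 both name that time.

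**3. Follow one subject.** Suppose a subject is discontinued in the unit at T40h and leaves. Section 10.3 calls for the early termination procedures before departure. Neither Section 9.1.9 nor the Table 1 column contains a laboratory test, so none is required. A result then exists only if the investigator takes an additional sample under Section 12.5.1, which is permitted after an abnormal result or when symptoms call for it. No post-dose draw is scheduled before T96h, so no scheduled abnormal result can prompt one, and a change without symptoms prompts nothing.

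**4. What does the SAP do with such a subject?** The shift count pairs screening with T96h and has no rule for an earlier value. SAP 8.2 plans no imputation of safety data beyond adverse event dates, relationship and severity. The subject drops out of the shift table; a discretionary result, if taken, would appear in the listing.

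**5. Size.** Inputs: N = 144 and 36 per arm (Protocol 15.2). The proportion p who leave before T96h is not stated; I assume 1% to 10%. Expected number without a required post-dose result = 144p in total and 36p per arm. Chance of at least one in the trial = 1 − (1 − p)^144, treating subjects as independent.

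| p (assumed) | 144p | 36p | at least one of 144 |
|---|---|---|---|
| 1% | 1.44 | 0.36 | 76% |
| 2% | 2.88 | 0.72 | 95% |
| 5% | 7.2 | 1.8 | over 99% |
| 10% | 14.4 | 3.6 | over 99% |

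One subject is 1/36 = 2.8% of an arm. These counts are upper limits for subjects with no post-dose result at all, because discretionary samples would supply some.

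**The case against.** The strongest reply is that the plan already covers most of these subjects. The synopsis, Protocol 15.3 and SAP 2.2 say that subjects who elect to discontinue in the inpatient phase will be asked to continue assessments through T96h unless they withdraw from everything, and the T96h draw is one of those assessments. Section 12.5.1 allows symptom-driven samples, which covers much of the adverse-event case. Footnote 8 speaks of discharge and could be read to include an early one. Section 9.1.9 is not a complete list: it also omits X-ray, NRS, PGE and IGE, all marked at early termination in Table 1. A mark in the table cannot reach a subject who refuses all further procedures, and Protocol 15.7 plans no formal safety comparisons.

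Much of this stands, and it rules out two stronger readings. A reader might infer that a subject who leaves early has no post-dose laboratory result at all. The documents do not support that, because a discretionary sample or a stay through T96h would give one. A reader might also infer that the adverse-event thresholds in 12.5.1 can never apply to such a subject. They are not limited to the T96h sample, so a discretionary sample would bring them into play.

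What the reply does not remove is the missing requirement. The request to stay is only a request, and it is written for subjects who elect to discontinue. For those removed for other reasons, Section 10.3 asks for follow-up procedures without naming laboratory tests. The discharge wording in footnote 8 is at best ambiguous beside its own window and beside footnote 4. The silence of 9.1.9 is weak evidence alone, but the blank cells in Table 1 and the wording of 12.5.1 point the same way.

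**Conclusion.** The point holds in a limited form. No post-dose hematology, chemistry or urinalysis is required for a subject who leaves before T96h, and this sits poorly with the synopsis statement that safety assessments are done at early termination. Subjects who leave after T96h are unaffected, as are discontinued subjects who stay and have the T96h draw. With an assumed departure rate of 1% to 10%, the gap concerns about 1 to 14 of 144 subjects, or 0.4 to 3.6 per arm. The rate is an assumption; the documents give none.

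It is tempting to go on to a probability that an abnormal value is missed. That would need a per-subject rate of new out-of-range values, which the documents do not give, and an out-of-range value is not the same as a clinically significant or drug-related one. The point is a cheap improvement to the safety data. It does not affect the efficacy analysis.

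**What to change.** In the protocol:
- Mark hematology, chemistry and urinalysis in the Early Termination column of Table 1 and add them to Section 9.1.9, with the condition *if the subject leaves the inpatient unit before the T96h sample and agrees to the draw*.
- Align footnote 8 and Section 12.5.1 with that condition.
- Keep the T96h draw for any discontinued subject who remains for assessments through T96h. Do not write the rule as T96h or discontinuation, whichever comes first: that would replace the T96h sample with an earlier one in a subject who stops but stays.

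In SAP 8.8, either include the early termination result as the last post-dose value in the change and shift summaries, flagged with its actual time, or show it on a separate early termination row.

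The cost is small. It is the draw already planned for every subject, taken earlier in the few who leave and agree. The drawback is that a few values come from an earlier postoperative time than T96h; the flag or the separate row makes that visible. Subjects who refuse all further procedures will still have no value.

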**6. LIST OF ABBREVIATIONS AND DEFINITION OF TERMS**

Abbreviation	Term
AE	Adverse event
ALT	Alanine aminotransferase
ANCOVA	Analysis of Covariance
aPTT	Activated partial thromboplastin time
ASA	American Society of Anesthesiologists
AST	Aspartate aminotransferase
AUC	Area Under the Curve
BID	Bis in die (twice daily)
BLQ	Below limit of quantitation
BP	Blood Pressure
BUNX	Bunionectomy
CA-008	Investigational product
CA-101	Cyclic urea
CFR	Code of Federal Regulations
CK	Creatine kinase
CL	Clearance
C max	Maximum plasma concentration
CNS	Central nervous system
CRF	Case Report Form (may include electronic data capture systems or paper forms)
CRO	Contract research organization
CS	Clinically significant
CSA	Clinical Study Agreement
D# or D-#	Day # (study days after surgery), Day # prior to surgery
DBP	Diastolic Blood Pressure
DIP	Distal interphalangeal
DMC	Data Monitoring Committee
DVT	Deep Venous Thrombosis
ECG	Electrocardiogram
EDC	Electronic data capture
ET	Early Termination
FCBP	Female of child bearing potential
FDA	Food and Drug Administration

Abbreviation	Term
FIH	First-In-Human
FCBP	Female of child-bearing potential
FSH	Follicle Stimulating Hormone
G	Gram
GCP	Good Clinical Practice
GGT	Gamma-glutamyl transferase
GLP	Good Laboratory Practice
H or HRS	Hours
HCl	Hydrochloride
HCU	Health care utilization
HED	Human Equivalent Dose
HEENT	Head, Eye, Ear, Nose and Throat
ICF	Informed consent form
ICH	International Conference on Harmonisation
IEC	Institutional Ethics Committee
IGE	Investigator Global Evaluation
INR	International Normalized Ratio
IRB	Institutional Review Board
ITT	Intent-to-treat
LDH	Lactate dehydrogenase
LLOQ	Lower limit of quantitation
LOE	Lack of efficacy
mcg or $\mu$	Microgram
MED	Morphine equivalent dose
MedDRA	Medical Dictionary for Regulatory Activities
Mg	Milligram
min	Minutes
mL	Milliliter
NCS	Not clinically significant
NOAEL	No Observed Adverse Effect Level
NRS	Numeric Rating Scale of Pain Intensity
NSAID	Nonsteroidal anti-inflammatory drug
OC	Opioid consumption in morphine equivalent dose
OF	Opioid-free days

Abbreviation	Term
OTC	Over-the-counter
PE	Physical examination
PGE	Patient Global Evaluation
PHN	Postherpetic neuralgia
PI	Principal Investigator
PK	Pharmacokinetic[s]
PO	Per oram (oral)
PRN	Pro re nata (as needed)
PT	Prothrombin time
QID	Quater in die (four times daily)
RBC	Red blood cell
SAE	Serious adverse event
SAP	Statistical analysis plan
SBP	Systolic blood pressure
SC	Subcutaneous
SD	Standard deviation
SE	Standard error
SOC	System Organ Class
SNRIs	Serotonin-norepinephrine reuptake inhibitors
SSRIs	Selective serotonin reuptake inhibitors
T#	Time in hours after completion of study medication dosing (T0)
t ½	Elimination half-life
TEAEs	Treatment emergent adverse event[s]
TID	Ter in die (three times daily)
T max	Time to maximum plasma concentration
TRPV1	Transient receptor potential vanilloid-1
TFR	Time to first rescue
UDS	Urine drug screen[ing]
US	United States
V	Volume of distribution
W#	Week # visit after surgery
WHO	World Health Organization

